9. SECONDARY ENDPOINT ANALYSES

9.1 Adherence

For the secondary endpoint of adherence, all mothers will be included. A secondary sensitivity analysis will be conducted including only mothers with drug concentration results for at least one visit after Enrollment.

For women randomized to the VR arm, a combination of measures will be used to characterize use of study product. In addition to the summary of maternal plasma DPV concentrations as described above in section 8.3, the residual DPV levels in the returned used rings will be summarized by study visit.

For women randomized to Truvada, maternal FTC-TP and TFV-DP concentrations from DBS sample collections, as described above in section 8.3, will be used to quantify study product use.

Cut-point Analyses

Drug levels will be summarized (number and percent) by categories defined by the following cut-points for each product. Because DPV ring release rates have not been verified against directly observed use, the only comparable category for the two products is no use.

DPV ring:

No use (rate \leq 0.9mg/month)
Some release (0.9mg/month $<$ rate \leq 4.0mg/month)
High release (rate $>$ 4.0mg/month)

Truvada:

No use (<16.6fmol/punch)
Some use (16.6-699fmol/punch)
High use (\geq 700fmol/punch)

DPV release rate is defined as the amount of DPV released from the ring divided by the duration of time during which the participant had the ring. The amount of DPV release is calculated by subtracting the

amount of residual DPV in a returned ring from the amount of DPV in control rings from the same lot number.

The number and proportion of participants visits with concentrations indicative of non-adherence (no use) will be compared by study arm using generalized estimating equations (GEE) with a Poisson link, an offset of number of tests for drug concentration, an exchangeable correlation structure and robust errors. The comparisons will be done using the cut-point levels described above for the two study arms: 1) residual ring data for participants assigned to the VR arm and 2) plasma data for participants assigned to Truvada. Trends over time in study product use will be explored using GEE.

This analysis differs slightly from the protocol in two ways. First, since the protocol was written, Dapivirine ring release has become the standard objective measure for vaginal ring use; therefore, Dapivirine plasma levels have been removed from the definition. Second, the outcome will be non-adherence (no use) rather than consistent study product use. No use is the only level of concentration results that are comparable between the two measures of product use. This is also more standard in adherence analyses since the protocol was written.

Reasons for study product non-use will be tabulated by arm. For women randomized to the VR arm, a summary with ring outages collected on the Ring Adherence eCRF will be presented by site. The summary will include ring outage reasons for removals and expulsions, the frequency of outages, and whether any outages were more than 12 hours. For women randomized to Truvada, a summary of missed pills by self-report from the Tablet Adherence eCRF will be presented. The summary will include the number of times per week the participant took the pill (0-7 days), how often the participant skipped the pill (never, rarely, often), and the reasons for not taking the pills.

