10.8.3 Analysis of Secondary Endpoints

Adherence: For women randomized to the VR arm, a combination of measures (maternal plasma DPV concentration and residual DPV levels in returned rings) will be used to characterize use of study product. For women randomized to Truvada, maternal plasma concentrations of drug will be used to quantify study product use. The number and proportion of participants visits with concentrations indicative of consistent study product use will be compared by study arm using generalized estimating equations (GEE) with a Poisson link and offset of number of tests for drug concentration. Trends over time in study product use will be explored using generalized estimating equations (GEE). Reasons for study product non-use (i.e. ring removal, missed pills) will be tabulated by arm.

Acceptability: To assess acceptability of the study products, information about acceptability will be obtained from questionnaires in which the participants will rate acceptability on a combination of categorical and continuous scales. Continuous measures of acceptability will be compared across arms using a t-test while categorical measures will be compared using chi-squared tests or Fisher's exact test, as appropriate. The number and percentages of participants who report the study product to be at least as acceptable as other HIV prevention methods will be summarized by study arm. These binomial proportions will be used to assess the acceptability of the study products along with the corresponding 95% confidence intervals and will be compared using chi-squared tests or Fisher's exact test, as appropriate.

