2.3 Randomization

Participants were randomized in a 3:1 ratio (VR:tablet) to the two arms of the study stratified by study site. The randomization scheme was generated and maintained by the MTN SDMC.

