2.5 Sample Size and Power

The target sample size was 200 mother-infant pairs randomized 3:1 to vaginal ring vs oral Truvada. A total of 197 mother-infant pairs were enrolled. The sample size is based upon feasibility, anticipated low drug concentrations, and the likelihood of a favorable safety profile. The statistical properties of the study are described using the probability of observed safety events defined in the primary endpoint. The probabilities of observing a safety event for various “true” event rates were calculated. For example, if the true safety event rate was 5%, the probability of observing zero safety events is 0.05% for the cohort size of 150 participants (DPV VR) and is 7.69% for cohort size of 50 participants (Truvada). An alternative way of describing the statistical properties is in terms of 95% confidence interval. For example, if none of the participants experience a safety event, the 95% exact 2-sided upper confidence bound for the true event rate is 2.43% for participant receiving the VR regimen and is 7.11% for participants receiving Truvada. The properties above also inform the hypotheses around drug detection where number of events is the number of participants with detectable drug levels. Further details of the statistical properties for this study are described in section 10.5 of the protocol.

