5. GENERAL ANALYSIS METHODS

Descriptive statistics will be used to assess group characteristics or differences by study arm. Categorical variables will be summarized using the number and percent in each category. The Pearson-Clopper method¹ will be used to obtain a 95% confidence interval (CI) on the proportion of binary variables where applicable. Continuous variables will be summarized using the number of non-missing values, mean, median, standard deviation, quartiles and range (minimum, maximum) unless otherwise indicated.

The study arms will be identified and formatted as "DPV vaginal ring" and "Truvada oral tablet".

When use of formal testing to assess differences is required, the following methods will be used unless otherwise specified: Fisher's exact test or logistical linear regression for categorical response variable; t-test or linear regression for continuous outcomes. Hypothesis tests for the primary and secondary endpoints comparing the two study arms will have a two-sided significance level of 5%.

Within study arm assessment of the change from baseline measurement to a follow up measurement will be analyzed using McNemar's test (for categorical response variables) or the paired t-test or Wilcoxon signed-rank test (for continuous variables).

To assess the adequacy of the randomization, participants in each of the two arms will be compared for baseline characteristics including demographics and laboratory measurements using descriptive statistics. No formal statistical comparisons will be performed.

As mentioned previously, there may be more than the usual amount of missing data in this study. Appropriate methods will be used to characterize and adjust for missingness as described in Section 3.2 above.

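### If exactly one arm has no no-use visit, the planned adherence GEE gives a meaningless p-value near 0, and the SAP has no fallback

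*SAP*

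**What the plan says.** SAP 9.1 sorts ring release rates and Truvada drug levels into three categories and compares the lowest, no use, between arms by "GEE) with a Poisson link, an offset of number of tests for drug concentration, an exchangeable correlation structure and robust errors". Protocol 10.8.3 already had this kind of model: visits "will be compared by study arm using generalized estimating equations (GEE) with a Poisson link and offset of number of tests for drug concentration". There the outcome was consistent use. SAP 2.0 changed it: "the outcome will be non-adherence (no use) rather than consistent study product use".

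SAP 5 sets the error level: "Hypothesis tests for the primary and secondary endpoints comparing the two study arms will have a two-sided significance level of 5" percent. It also offers "Fisher's exact test or logistical linear regression for categorical response variable", but only where nothing else is specified, and 9.1 specifies the GEE.

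The rest of 9.1 contains no second arm comparison. A sensitivity analysis narrows the set of mothers, time trends are explored, and reasons for non-use are tabulated. Nothing says what to do if an arm has no events, and no small-sample or exact alternative is given. SAP 9.2 uses Fisher's exact test for the binary acceptability comparisons.

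**The concern.** A log-link model estimates the log of a rate ratio. If one arm has no events, that quantity is minus or plus infinity, and software stops at a large finite number. A model-based standard error grows enormous and signals the failure. A robust (sandwich) standard error does not, because it is built from residuals, and in the empty arm these shrink in step with the fitted mean. The result is a huge estimate over an ordinary standard error, and the software still reports convergence.

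Under 3:1 allocation the Truvada arm is small, and the outcome is now the lowest use category. If adherence is good in both arms, the trial could report that one product is significantly better adhered to on the strength of a single affected woman.

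**Working it through.** **Inputs.** "A total of 197 mother-infant pairs were enrolled" (SAP 2.5), and "Participants were randomized in a 3:1 ratio (VR:tablet) to the two arms of the study stratified by study site" (SAP 2.3). The split by arm is not given; 197 × 3/4 = 147.75, so 148 ring and 49 Truvada women are assumed. Rings are returned at Visits 5, 6 and 7 (Protocol Appendix I), giving 3 tests. Maternal dried blood spots are taken after Enrollment at Visits 3-8 (SAP 8.3), giving 6 tests, or 5 without the post-product Visit 8. The no-use rate and within-woman correlation are assumptions.

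**The plan's own zero-event figure.** SAP 2.5 gives the chance of no event at a 5% true rate. (1 - 0.05)^150 = 0.05% and (1 - 0.05)^50 = 7.69%; both reproduce. The documents give no such figure for adherence.

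**Why the standard error stays finite.** With equal numbers of tests within an arm, the robust variance of an arm's log rate is Σ(yᵢ - μ)² / (Σμ)², where yᵢ is a woman's no-use count and μ the fitted mean per woman.
- Arm with e of n women having one event each: 1/e - 1/n.
- Empty arm: every residual is -μ, so nμ²/(nμ)² = 1/n, however small μ becomes.

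Ring 1 of 148, Truvada 0 of 49: 1 - 1/148 + 1/49 = 1.0137, so SE = 1.007. Ring 3 of 148, Truvada 0 of 49: 1/3 - 1/148 + 1/49 = 0.3470, so SE = 0.589. Both match the fitted values below.

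**Fitted model** (Poisson GEE, exchangeable, robust; 3 ring and 5 Truvada tests), against Fisher's exact test on women with any no-use:

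| Ring women affected | Truvada women affected | GEE Wald p | Fisher p |
|---|---|---|---|
| 1 | 0 | about 1e-97 (log rate ratio -21.1, SE 1.007) | 1.0 |
| 2 | 0 | about 1e-208 | 1.0 |
| 3 | 0 | 0 to machine precision | 0.575 |
| 0 | 1 | about 1e-116 | 0.249 |
| 3 | 1 | 0.66 | 1.0 |

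Once each arm has an event, the test behaves. A bias-reduced sandwich does not help (1 ring woman affected: SE 1.014, p < 1e-85).

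**How easily an arm is empty.** If k women in all are ever no-use and the arms do not differ, the chance that all k are in the ring arm is C(148,k)/C(197,k): 75%, 56%, 42% and 32% for k = 1, 2, 3 and 4. The chance that none of 49 Truvada women is affected is (1 - q)^49, where q is the share of women ever no-use: 61% at q = 1%, 37% at 2%, 8% at 5%, 0.06% at 14%.

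**Type I error** by simulation with equal true rates, 148 and 49 women, 3 ring and 5 Truvada tests, correlation 0 to 0.5, robust Wald test at nominal 5%:

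| No-use per visit | Type I error |
|---|---|
| 0.5% | 34-54% |
| 1% | 11-38% |
| 2% | 4-15% |
| 5% or more | 4-7% |

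The excess comes mainly from empty arms. With 6 Truvada tests, correlation 0.3 and 1% no-use, type I error was 23.8%: 18.6 points with only the Truvada arm empty, 3.1 with only the ring arm empty, and 2.1 with events in both arms.

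**The case against.** **No-use may not be rare.** A reader might infer from the move to the lowest category that the outcome is sparse. The documents do not say so. Their only background figures are for earlier oral PrEP trials: detectable drug in 24-82% of participants (Protocol 2.8.2), and from under 30% to 86% by plasma level (Protocol 2.10.2). These imply at least 14% undetectable, where an empty Truvada arm is very unlikely. They are serum or plasma results from other trials, not this dried-blood-spot cut-point over 12 weeks, so they do not settle the rate. The point must stay conditional.

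**The SAP does not say Wald.** It says only robust errors. Wald is the usual output, but a robust score test on the same data, with no Truvada events, gives p of about 0.32, 0.16 and 0.08 for 1, 2 and 3 affected ring women. That is not near 0, though with 3 it is still far below Fisher's 0.575. This stands: the statistic has to be named.

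**An analyst would notice.** Counts are tabulated by arm, and a log rate ratio near -21 looks wrong. That is likely, but the SAP gives the analyst no other test, and one chosen after seeing the data is not pre-specified.

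**Little depends on it.** Adherence is secondary, its objective is to characterize use, and the primary analyses are descriptive. This limits the severity but does not make the p-value valid.

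**Replacing the test in every case would go too far.** This also stands. The fault lies in empty arms, and permuting each woman's proportion of no-use tests would mix proportions based on 3 tests with others based on 5 or 6.

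**Conclusion.** The concern holds as a conditional fault. Whenever exactly one arm has no no-use visit, the specified model with its usual Wald test gives a p-value near 0 that carries no information about the difference, and the SAP provides no alternative. If both arms are empty, no rate ratio can be estimated.

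The overall effect depends on a no-use rate the documents do not give. Type I error is badly inflated at 0.5-1% per visit, may be inflated at 2%, and is close to nominal from 5%. These figures rest on the 148/49 split, 3 and 5 tests per woman, correlation of 0 to 0.5 and the Wald reading. A reader might conclude that the adherence comparison is generally invalid or that a false positive is to be expected. The documents do not support that, because the test behaves acceptably at higher no-use rates. No primary conclusion is affected, but SAP 9.1 should be corrected.

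**What to change.** In SAP 9.1:

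1. Name the test statistic used with the GEE.
2. Keep the GEE rate ratio and p-value when both arms have at least one no-use visit.
3. If either arm has none, report no GEE rate ratio or Wald p-value. Report, per arm, the number of women with any no-use and an exact 95% confidence interval, and compare arms with Fisher's exact test at participant level, as in SAP 9.2. Count only Visits 5-7 in this fallback, so that both arms have three scheduled tests per woman.

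The cost is a few sentences of SAP text and a few lines of code, with no change to data collection. In the fallback case there is no model-based rate ratio, and Truvada tests outside Visits 5-7 are not used. With 0 of 49 Truvada women affected, Fisher's p is still 0.116 at 9 of 148 ring women, so the fallback will often be inconclusive, which is a fair reflection of so few events.

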7.10 Drug Detection and Biomarker Collection

The mother-infant pairs will provide specimens for drug detection and biomarkers throughout this study. At Visit 2, all mothers will provide DBS for FTC-TP and TFV-DP. Following enrollment, mother and infant drug detection will be stratified by study product assignment as specified in Table 17 and Table 18 below. Vaginal swabs for microbiota and biomarkers will be collected from mothers at Visit 2, Visit 7 and the Early Termination Visit. Details on blood sampling procedures for mothers and infants, inclusive of capillary/venous blood usage for DBS procedures, as per site procedures, will be included in the *MTN-043 SSP Manual*.

Table 17: Drug Detection and Biomarkers Specimen Collection Schedule – Mothers

Visit	Specimens Collected for Drug Detection	Specimens Collected for Microbiota & Biomarkers
Visit 2 – Enrollment	
 DBS for FTC-TP & TFV-DP (DPV & Truvada groups) 	
 Vaginal swab for microbiota Vaginal swab for biomarkers Vaginal swab for Gram stain
Visit 3 – Week 1 Visit 4 – Week 2	
 Plasma for DPV (DPV group) Breast milk for DPV (DPV group) DBS for FTC-TP and TFV-DP (Truvada group) Breast milk for FTC and TFV (Truvada group) 	
Visit 5 – Month 1 Visit 6 – Month 2 Visit 7 – Month 3 (PUEV) Visit 8 – 2 weeks after PUEV (SEV) Early Termination	
 Plasma for DPV (DPV group) Breast milk for DPV (DPV group) DBS for FTC-TP and TFV-DP (Truvada group) Breast milk for FTC and TFV (Truvada group) 	
 Vaginal swab for microbiota* Vaginal swab for biomarkers* Vaginal swab for Gram stain*

* Visit 7 and Early Termination Visit only

Table 18: Drug Detection and Biomarkers Specimen Collection Schedule – Infants

Visit	Specimens Collected for Drug Detection	Specimens Collected for Microbiota & Biomarkers
Visit 4 – Week 2		
Visit 5 – Month 1		
Visit 6 – Month 2		
Visit 7 – Month 3 (PUEV)		
Visit 8 – 2 weeks after PUEV (SEV)	
 • Plasma for DPV (DPV group) • DBS for FTC-TP and TFV-DP (Truvada group) 	
Early Termination		

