15 APPENDICES

APPENDIX I: Table of Visits and Study Procedures – Mothers

	Visit 1 SCR	Visit 2 ENR	Visits 3,4 (Week 1, 2)	Visits 5, 6 (Month 1, 2)	Visit 7 (Month 3 PUEV)	Visit 8 SEV (2 weeks after PUEV)	Early Termination Visit
ADMINISTRATIVE AND REGULATORY							
Obtain/confirm informed consent	^	X					
Assess and/or confirm eligibility	X	X					
Collect demographic information	X						
Randomization		X					
Collect/review/update locator information	X	X	X	X	X	X	X
Assign a unique PTID number	X						
Obtain signed medical records release and pediatric care provider information	X						
Provide reimbursement	X	X	X	X	X	X	X
Schedule next visit/contact	*	*	X	X	X	*	*
BEHAVIORAL							
HIV pre-/post-test counseling	X	X	*	X	X		X
HIV/STI risk reduction counseling	X	X	*	X	X	*	X
Contraception counseling	X	X	*	X	X	X	X
Behavioral assessment		X	X	X	X		X
Product acceptability assessment		X	X	X	X		X
Protocol adherence counseling		X	X	X	X		
Social harms assessment			X	X	X	X	X
In-depth interview (IDI) (subset)					♦		X
PrEP counseling						X	X
CLINICAL							
Infant feeding assessment	X	X	X	X	X		X
Concomitant medications and vaginal products	X	X	X	X	X	X	X
Review/update medical history	X	X	X	X	X	X	X
Physical exam (Targeted after Screening Visit)	X	X	*	*	X	*	X
Pelvic exam	X	X	*	*	X	*	X
Collect AEs	*	▼	*	X	X	X	X
Treat STIs/RTI/UTI	*		*	*	*	*	*

		Visit 1 SCR	Visit 2 ENR	Visits 3,4 (Week 1, 2)	Visits 5, 6 (Month 1, 2)	Visit 7 (Month 3 PUEV)	Visit 8 SEV (2 weeks after PUEV)	Early Termination Visit
Disclose available test results		X	X	X	X	X	X	X
LABORATORY								
URINE	Pregnancy test	X	X	*	*	X	*	X
	Urine dipstick and/or culture	*	*	*	*	*	*	*
BLOOD	HIV-1 testing	X	X	*	X	X	*	X
	AST/ALT	X		*	*	X	*	X
	Creatinine clearance	X		*	*	X	*	X
	Complete blood count (CBC) with platelets	X		*	*	X	*	X
	Syphilis serology	X	*	*	*	*	*	*
	Plasma archive		X					
	HBsAg	X						
	Plasma for DPV drug levels (DPV group)			X	X	X	X	X
	DBS for FTC-TP & TFV-DP drug levels (Truvada group)		X (Both DPV & Truvada groups)	X	X	X	X	X
BREAST MILK	Breast milk for DPV drug levels (DPV group)			X	X	X	X	X
	Breast milk for FTC and TFV drug levels (Truvada group)			X	X	X	X	X
PELVIC	NAAT (GC/CT/TV)	X	*	*	*	*	*	*
	Wet prep/KOH wet mount for candidiasis and/or BV	*	*	*	*	*	*	*
	Vaginal pH	*	*	*	*	*	*	*
	Vaginal swab(s) for microbiota		X			X		X
	Vaginal Gram stain		X			X		X
	Vaginal swab(s) for biomarkers		X			X		X
STUDY PRODUCT	Adherence Assessment: Returned study VR				X	X		X
STUDY PRODUCT								

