8.3 Drug Detection

The proportion of participants with detectable drug levels in each study arm for each sample type will be summarized using descriptive statistics in tables by arm and by site. Participants with a drug level for the assigned study product arm above the lower limit of quantification (LLOQ) for any visit after Enrollment will be considered to have a detectable drug level; otherwise, the participant will be considered to have an undetectable drug level.

Drug concentration levels will be summarized using geometric mean, geometric coefficient of variation (CV), arithmetic mean, standard deviation (SD), median, interquartile range (IQR), and range (minimum, maximum). In addition, the number and percentage of participants with detectable and undetectable drug levels will be reported. The CV will be calculated as $100 \times \text{standard deviation (SD)} / \text{Mean of the concentration values}$. Figures for concentration values will be presented using the log scale.

For drug concentrations that fall below the corresponding assay's LLOQ, we will use a value equivalent to half the LLOQ. The number of days to each sample collection will be calculated using the Enrollment date and the date of sample collection as reported in the drug concentrations dataset from the SCHARP Lab Data Management group. For mothers, the time points for drug concentration sample collections are on Visits 3-8 (Week 1 to 2 weeks after product use end visit [PUEV]). Dried blood spot (DBS) samples are collected from mothers at Visit 2, Enrollment in addition to Visits 3-8. For infants, the time points for drug concentration sample collections are on Visits 4-8 (Week 2 to 2 weeks after PUEV).

For the mothers on the DPV VR arm, concentrations of DPV from plasma and breast milk will be reported for each visit in a table by study site. For infants of mothers on the DPV VR arm, concentrations of DPV from plasma will be reported for each visit in a table by study site. Box plots with median DPV levels of plasma concentrations for mothers and infants and of breast milk concentrations for mothers will be presented over the study visit timepoints.

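### SAP 9.1's between-arm adherence test names a Truvada sample that no visit schedules, leaves the analyte open, and does not exclude off-product tests

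*SAP*

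**What the plan says.** SAP 9.1 compares the proportion of tests classed as no use between arms. It uses a Poisson GEE with the number of tests as offset, an exchangeable correlation and robust errors. SAP 5 sets a two-sided 5% level for such tests.

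- **Input named in the comparison.** Residual ring data for the ring arm, and "2) plasma data for participants assigned to Truvada".
- **Input named earlier in SAP 9.1.** "maternal FTC-TP and TFV-DP concentrations from DBS sample collections, as described above in section 8.3, will be used to quantify study product use". The Truvada category is "No use (<16.6fmol/punch"), a per-punch unit. No analyte is attached to it or to the 700 cut-point.
- **Protocol analysis text (10.8.3).** "For women randomized to Truvada, maternal plasma concentrations of drug will be used to quantify study product use". Protocol 2.11 also says that Truvada plasma levels will be collected.
- **What is scheduled.** Protocol Table 17 (section 7.10) lists "DBS for FTC-TP and TFV-DP (Truvada group") and breast milk. Appendix I agrees. SAP 6.4 expects plasma drug levels in the ring arm only.
- **When DBS is taken.** SAP 8.3: "samples are collected from mothers at Visit 2, Enrollment in addition to Visits 3-8".
- **When rings are tested.** The Appendix I row "Adherence Assessment: Returned study VR" is marked at Visits 5, 6 and 7 and at early termination.

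**The concern.** There are two problems.

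First, the input is misnamed and incomplete. Two analytes are measured in DBS, and the cut-points are tied to neither. Two analysts following SAP 9.1 could therefore classify the same mother differently. SAP 9.1 lists two departures from the protocol, and a change from plasma to DBS is not one of them.

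Second, the visits that feed the model are not listed. A Visit 8 DBS below the cut-point would count as non-adherence although the product had been taken back as planned. No ring test can be affected in that way. The offset corrects for how many tests a mother had, not for when they were taken.

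This is the plan's only between-arm test of an objective adherence measure. In an open-label trial, leaving the visits and the analyte open allows both to be chosen after results are seen.

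**Working it through.** The documents give no power or effect size for this comparison, so there is no planned figure to reproduce. The check is a count of scheduled tests, followed by arithmetic on assumed rates.

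**Step 1: matrix.** The maternal visit tables, Table 17, Appendix I and SAP 6.4 contain no Truvada plasma drug level. The other plasma items are the Enrollment archive and collection after a positive HIV test. Neither is a scheduled Truvada drug-level sample.

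**Step 2: visits.**

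| | Ring | Truvada DBS |
|---|---|---|
| Scheduled post-enrollment tests | 3 (Visits 5, 6, 7) | 6 (Visits 3 to 8) |
| Of these, off product | 0 | 1 (Visit 8) |
| Adding baseline Visit 2 | not applicable | 7, of which 2 off product |

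Off-product share: 1/6 = 16.7%, or 2/7 = 28.6%. The SAP does have an exposed-visits restriction (section 3.1), but it is a secondary analysis introduced for drug concentrations, not for adherence. The adherence sensitivity analysis restricts mothers, not visits. Product holds add little, because Protocol 7.5.4 stops drug-level sampling after the hold visit.

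**Step 3: possible effect.** Let p be the true on-product no-use rate, equal in both arms, and q the share of Visit 8 DBS below 16.6 fmol/punch. Both are assumptions.

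- Visits 3 to 8: Truvada rate = (5p + q)/6, and apparent Truvada:ring ratio = (5p + q)/(6p).
- With Visit 2 counted as no use: Truvada rate = (5p + q + 1)/7, and ratio = (5p + q + 1)/(7p).

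For p = 0.10 and q = 0.5: (0.50 + 0.50)/6 = 0.167, and 0.167/0.10 = 1.67, where the true ratio is 1.00.

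| p | q = 0 | q = p | q = 0.5 | q = 1 | With Visit 2, q from 0 to 1 |
|---|---|---|---|---|---|
| 0.05 | 0.83 | 1.00 | 2.50 | 4.17 | 3.57 to 6.43 |
| 0.10 | 0.83 | 1.00 | 1.67 | 2.50 | 2.14 to 3.57 |
| 0.20 | 0.83 | 1.00 | 1.25 | 1.67 | 1.43 to 2.14 |

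**Step 4: false-positive rate.** The SAP model was simulated with equal true no-use, 600 runs per scenario. The assumed arm sizes were 148 and 49 mothers (197 enrolled, split 3:1), with a within-mother correlation of 0.3.

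| Truvada tests used | p = 0.10 | p = 0.20 |
|---|---|---|
| Visits 3 to 8, q = p | 5.5% | 5.3% |
| Visits 3 to 8, q = 0.5 | 57% | 23% |
| Visits 3 to 8, q = 1 | 100% | 94% |
| Visits 5 to 7 | 5.2% | 4.8% |

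With Visit 2 included, the rate was at least 80% in every scenario run.

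**The case against.** The strongest reply is that this is a wording slip with an obvious reading, and that the numbers above come from assumptions. Much of it stands.

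- **The matrix is recoverable.** SAP 9.1 itself points to DBS and per-punch cut-points. A reader might infer that the comparison cannot be run at all; the section does not support that. The analyte, however, cannot be recovered from the text.
- **Visits 3 and 4 are not off product.** A reader might infer that half of the post-enrollment Truvada tests (Visits 3, 4 and 8) have no ring equivalent. SAP 9.1 defines release over the time the mother had the ring, so the ring returned at Visit 5 covers the period containing Visits 3 and 4. Only Visit 8 falls outside any wear period.
- **Visit 2 is the weaker reading.** The protocol labels that DBS baseline and takes it in both arms, and SAP 8.3 defines detection by visits after Enrollment. SAP 9.1's main analysis has no such limit, so exclusion is likely but not stated.
- **No direction of bias is shown.** The ratio falls below 1 when q is less than p and rises above 1 when q exceeds p. A mother at 700 fmol/punch would have to fall 700/16.6 = 42-fold to read as no use. That is log2(42) = 5.4 halvings, so over 14 days it needs a half-life below about 14/5.4 = 2.6 days under first-order decay. No half-life is given for either DBS analyte. Mothers in the middle category (16.6 to 699) would need a smaller fall.
- **A Visit 8 effect would be visible.** Concentrations are tabulated by visit. That helps a reader see the effect, but it does not correct the test result.

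**Conclusion.** The point holds as a should-fix. The Truvada input to the comparison is misnamed, its analyte is unspecified, and the plain reading lets a scheduled off-product test count as non-adherence in one arm only. That affects 1 of 6 post-enrollment Truvada tests, or 2 of 7 on the less clear reading that includes Visit 2.

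A reader might go further and infer that the arm contrast must reflect the visit schedule rather than behaviour. The documents do not support that. The bias could be negligible or large, depending on the analyte and on how many Visit 8 samples fall below 16.6 fmol/punch, and neither is given. The ratios and false-positive rates rest on the assumed p, q, correlation and arm split. No primary endpoint depends on this comparison.

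**What to change.** 1. In SAP 9.1, replace plasma with DBS for the Truvada arm, and state whether the 16.6 and 700 fmol/punch cut-points apply to FTC-TP or TFV-DP. Align Protocol 10.8.3 and 2.11, and add the change to the SAP's list of departures from the protocol.
2. Restrict both outcome and offset to on-product tests. Exclude Visits 2 and 8 from the comparison and report them descriptively.
3. State that early-termination samples taken on product are kept in both arms. Both the returned ring and the DBS are collected at that visit, and mothers who stop early matter for a no-use outcome.
4. Choose the main set in advance. One option is Visits 5 to 7 plus on-product early termination in both arms. The other is to keep the Visit 3 and 4 DBS and run the matched set as a sensitivity analysis. Under the second option, 3 of 5 scheduled Truvada tests (Visits 3, 4, 5) fall in the first month against 1 of 3 ring tests, so a change in use over time would be weighted differently by arm.

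The cost is wording and a small loss of Truvada tests: 3 scheduled per mother in the matched set, or 5 with Visits 3 and 4, instead of 6. No new data are needed.
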